The cryoneurolysis mechanism of action is well-understood and established in prior studies.⁵ Results of a recent study demonstrate that cryoneurolysis can alleviate the pain and symptoms of knee OA for up to 90 days¹. Pharmacologic and surgical options for ankle OA are limited. Using cryoneurolysis in patients with ankle OA could potentially provide immediate symptomatic relief with a greater duration of analgesia and a lower rate of side effects. These potential benefits could reduce the need for both clinic and injection visits when compared to other available treatment modalities, thereby reducing patient and provider burden and health care expenditures.

II. Research Plan and Design

A. Study Objectives: The goal of this study is to evaluate the efficacy of cryoneurolysis for improving ankle symptoms and function. Specifically, this study will measure changes in pain, activities of daily living, quality of life and physical performance at 6, 12 and 24 weeks after each superficial and deep treatment.

B. Study Type and Design:

This is a single-site, open-label study of participants with painful ankle OA assigned to undergo cryoneurolysis of either the Superficial Fibular Nerve (SFN), Sural Nerve (SN) and Saphenous Nerve, or the Deep Fibular Nerve (DFN) using ultrasound-guided cryoneurolysis. Subjects will initially undergo diagnostic nerve blocks using 1% lidocaine with epinephrine for either the superficial nerves or the DFN to confirm analgesia prior to the cryoneurolysis procedure.

We will evaluate responder status with NRS at clinic visits 6 weeks, 12 weeks and 24 weeks following treatment as well as NRS via web-form or phone calls (per subject preference) at 3, 9 and 18 weeks. "Non-responders" being defined as anyone reporting less than 20% pain relief with respect to their baseline NRS scores. For subjects who become non-responders, we will treat the other nerve group with iovera at their next clinic visit (e.g. if a subject becomes a non-responder 9 weeks after superficial nerves are treated, then at 12 week follow-up, the participant will be offered treatment of the deep fibular nerve).

Figure 2 depicts the flow of how participants will be treated and potentially offered an alternative treatment if their initial treatment fails to provide durable benefit.

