FAOS (Pain, ADL, QoL), NRS for pain and physical performance tests (40 m fast paced walking test and, Standing Balance Test) will be assessed at baseline and 6, 12, and 24 weeks post-treatment. Phone calls at 3, 9 and 18 weeks post-treatment will monitor subjects using the NRS pain scale.⁷ Electronic data capture will be used for this study. Adverse events will be monitored at each telephone call and follow-up visit. There will be a grace period of 21 days between the screening and treatment visit. There is a +/- 3-day window for follow-up visits. During the time period of March to May, 2020(depending on duration of suspension of non-essential research), we are modifying the protocol to conduct virtual study visits to address the COVID-19 pandemic. The following data points will be or will not be collected during this time as per the individual circumstance: 40mFPWT or Standing Balance test at 6 week, 12 week, and 24 week. In order to ensure subject safety and welfare we will conduct the 6 week, 12 week and 24 week f/u visit remotely for each treatment arm as per KU essential research guidelines. We will also offer participants masks, gloves, and complete the f/u visit at the

earliest to limit any potential exposure to people in the hospital. In order to address data integrity issues, we will try to conduct the 12 week f/u visits in person.

[figure not shown]

Figure 2 – Protocol flowchart depicting criteria for responders and non-responders at each follow up time point.

C. Sample size and power calculation

In this open-label study, participants will undergo cryoneurolysis using iovera. FAOS (Pain, ADL, QoL), NRS for pain and physical performance tests (40m fast-paced walking test and Standing Balance Test) data will be collected at baseline and 6, 12 and 24 weeks post-treatment. A 24-week follow-up duration was selected to detect meaningful differences from standard of care and long-term effects. A control group will not be included in this initial pilot study. Differences between each of the three follow-up time points and baseline will be assessed using one-sample t-tests or repeated measures analyses, as appropriate, controlling for study-wide alpha level to account for multiple comparisons as well as 6-week and 24-week analyses.

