The following medications and nonpharmacological therapies may be taken or used throughout the study:

- Aspirin for cardio-protection at a maximum stable dose of 100 mg per day provided the dose was stabilized over 3 months prior to study entry.
- Physical therapy/bracing for the ankle joint if the program was initiated and consistent prior to study entry.
- Acetaminophen as an occasional rescue medication. Concomitant treatment for OA will be standardized to oral acetaminophen (e.g. Tylenol) for all subjects during the study. During the screening period (i.e., prior to the procedure visit), subjects may take acetaminophen as needed to a maximum of 3000 mg per day. Use of acetaminophen must be discontinued 48 hours prior to the procedure visit and each subsequent scheduled visit.
- The use of acetaminophen for other types of pain or illness during the study (e.g., toothache, headache, fever) should also be recorded.

5. Restricted Medications/Nonpharmacological Therapies

Patients will be asked to abstain from certain medications and therapies. The following medications and nonpharmacological therapies should not be taken or used beginning immediately upon enrollment (after signing informed consent) until the subject reaches the end of the study:

- Oral non-steroidal anti-inflammatory drugs (NSAIDs) (unless on a chronic stable dose for ≥ 3 months prior to enrollment).
- Topical analgesics applied to the skin over the index ankle (e.g., NSAID's, capsaicin, lidocaine, heat patches).
- Orally administered systemic corticosteroids (unless on a chronic stable dose for ≥ 3 months prior to enrollment).
- Intra-articular injection into the ankle or subtalar joints.
- Centrally acting pain medications (unless on a chronic stable dose for ≥ 3 months prior to enrollment).
- Opioid medications (unless on a chronic stable dose for ≥ 3 months prior to enrollment)

E. Specific methods and techniques used throughout the study

Primary Outcome

The Foot and Ankle Outcome Score (FAOS), derived from the validated Knee Injury and Osteoarthritis Outcome Score (KOOS). It is a region-specific questionnaire that has been well described and validated.^{9 11}

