The Standing Balance Test outcome is measured with the feet side by side, then in semi-tandem stance (heel of one foot in front and beside the big toe of the other foot), and then in tandem stance (heel of one foot directly in front of the other foot); each stance was held for up to 10s. These test results are converted to scores (range 0-4). Higher scores represent better function and a score of 0 represents the inability to complete the test. Subjects are given a score of 1 if they can hold a side-by-side standing position for 10 s but are unable to hold a semi-tandem position for 10s, a score of 2 if they can hold a semi-tandem position for 10s but are unable to hold a full tandem position for more than 2s, a score of 3 if they can stand in the full tandem position for 3-9s, and a score of 4 if they can stand in the full tandem position for 10s.¹³ The Standing Balance Test will be completed by the Subject and will take approximately 2 minutes to complete. The study coordinator or designee will enter the data into the eCRF.

The tables below depict the schedule of study assessments, or procedures, for each visit for the intervention(s) offered (superficial and/or deep).

Assessment	Visit 1 / Screening	Visit 2 / iovera[®] Treatment -1	Telephonic 3 Week Follow-up	Visit 3 / 6 Week Follow-up	Telephonic 9 Week Follow-up	Visit 4 / 12 Week Follow-up	Telephonic - 18 Week Follow-up	Visit 5 / 24 Week Follow-up
Informed Consent	X							
Eligibility	X	X						

Radiograph or SCT (if not previously done)	X							
Medical history	X	X						
Concomitant medications	X	X		X		X		X
Prior/Concurrent Therapy	X							
Study Treatment		X						
Physical Exam	X	X						
FAOS Questionnaire	X			X		X		X
NRS for Pain	X	X	X	X	X	X	X	X
Physical Performance Measures	X			X		X		X
AE/SAE Assessment		X	X	X	X	X	X	X

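### The first-course FAOS and performance baseline is, by inference, the screening visit, the only FAOS visit outside the 48-hour acetaminophen hold; a pre-procedure record at Visit 2 would align it with follow-up

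*Combined protocol and SAP*

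**What the plan says.** Section II.D.4 lets patients take acetaminophen as needed, up to a daily maximum, during the screening period. It then adds: "Use of acetaminophen must be discontinued 48 hours prior to the procedure visit and each subsequent scheduled visit". The inclusion criterion on pre-study analgesics (II.D.1) exempts acetaminophen, so it does not extend the hold back to screening.

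Section II.B says that FAOS, NRS and the performance tests "will be assessed at baseline and 6, 12, and 24 weeks post-treatment", without naming the baseline visit. In the first-course schedule (II.E), the row "FAOS Questionnaire" and the performance row are marked at screening and at weeks 6, 12 and 24. Both are blank at Visit 2, the treatment visit. In the second-course schedule both rows are marked on the treatment day.

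On timing, II.B states: "There will be a grace period of 21 days between the screening and treatment visit". The screening FAOS also serves the entry criterion of a score below 75 in at least one category (II.D.1). Section II.C states: "A control group will not be included in this initial pilot study".

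Two related references are left open. Section V.A compares follow-up with baseline for each intervention and does not say which record is the second-course baseline. Section II.B defines a non-responder as "anyone reporting less than 20% pain relief with respect to their baseline NRS scores" and does not name the visit or the question.

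**The concern.** In an uncontrolled trial the baseline is the only comparator, and Specific Aim 1 asks for the extent of pain relief. Any systematic difference in how baseline and follow-up are recorded therefore goes straight into the estimate. Here the first-course baseline may be recorded with acetaminophen on board, while every follow-up FAOS is recorded after a 48-hour hold.

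Two influences pull in opposite directions. Acetaminophen taken before screening would tend to lower baseline pain and so understate improvement. Using a visit at which patients are selected for poor scores would tend to overstate it through regression to the mean. The documents size neither. For the performance tests only the first applies directly, because they are not entry criteria.

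The stake is a biased estimate of change, not a lost test of the primary endpoint.

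**Working it through.** **1. Visits against the hold (II.E schedules and II.D.4)**

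| Visit | FAOS and performance tests | 48-hour hold |
|---|---|---|
| Screening | yes | no |
| Visit 2 (first treatment) | no | yes |
| Weeks 6, 12, 24 | yes | yes |
| Second-treatment day | yes | yes |
| Weeks 6, 12, 24 of the second course | yes | yes |

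Only one first-course record precedes treatment, so screening is the baseline by elimination. It is the only row with FAOS and no hold.

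**2. How much of each measure the hold reaches**

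- Items P2 to P9 (eight of the nine pain items, II.E) ask about the last week. The hold covers 2 of 7 days, or 29% of that window.
- P1 asks about frequency and states no window.
- The 40 m walk and the balance test are done on the day, so the hold bears on them fully.

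**3. Illustration of size**

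The documents give no shift, so those used here are assumptions. The plan's own figures supply only n: 32 / (1 − 0.20) = 40 recruited (II.C), hence 32 evaluable.

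- Standard error of mean change = 1/√32 = 0.177 SD.
- 95% half-width = 2.0395 × 0.177 = 0.361 SD (t, 31 df).
- With a baseline shift of s SD, coverage = P(|T| < 2.0395), where T is noncentral t with noncentrality s√32.
- s = 0.1: noncentrality 0.566, coverage 91.5%.
- s = 0.2: noncentrality 1.131, coverage 80.5%.

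For scale, one answer step on one pain item is 100/36 = 2.78 points. If the SD of change is 15 to 25 points (assumed), that is 2.78/15 = 0.19 SD to 2.78/25 = 0.11 SD.

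**4. Power for FAOS-Pain**

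Section II.C cites an effect size of 1.06, taken here as SDs of change, which the protocol does not specify. Suppose a shift of 0.3 SD against benefit. The effect is then 1.06 − 0.3 = 0.76, and the noncentrality is 0.76 × √32 = 4.30. Power at one-sided 0.025 is 98.6%.

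**5. The NRS reference**

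NRS is marked at screening and at Visit 2, with two questions each time (past 7 days, right now): 2 × 2 = 4 candidate baselines. The choice can change status. A follow-up score of 5 is (6 − 5)/6 = 16.7% relief from a baseline of 6, a non-responder. From a baseline of 7 it is (7 − 5)/7 = 28.6%, not a non-responder. The consequence is stated in II.B: "For subjects who become non-responders, we will treat the other nerve group with iovera at their next clinic visit". After the week-3 call, the next clinic visit is week 6, before the 12-week primary assessment.

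**6. Time needed for a Visit 2 record (II.E timings)**

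FAOS Pain, ADL and QoL take 3 + 4 + 2 = 9 minutes, and the two tests take 2 + 2 = 4 minutes. That is 13 minutes per patient, and 13 × 40 = 520 minutes, or 8.7 hours, in all.

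**The case against.** The strongest reply is that a screening baseline is an ordinary design choice. There is only one pre-treatment record, so nothing is contradictory. The two biases oppose each other, 21 days is a maximum, and no passage suggests a shift of 0.1 SD or more. A mean shift of 2.78 points would need the average patient to move one full step, net, on one item, from a hold covering two of seven recall days. This stands, and it limits the point to an inexpensive improvement.

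A second reply is that Visit 2 has problems of its own. Eligibility is marked there as well as at screening, so selection on FAOS would be reduced rather than removed. Answers given on the procedure day may reflect anticipation. The protocol also says "Subjects will initially undergo diagnostic nerve blocks using 1% lidocaine with epinephrine", but no schedule row dates the block. One given in the week before Visit 2 would fall inside the recall window, and screening would then be the cleaner record. This stands too, and it is why the fix keeps the screening value in a sensitivity analysis and asks for the block date.

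A reader might infer that the unnamed second-course baseline leaves the primary analysis undefined. The documents do not support that. The endpoint is set 12 weeks after each treatment (I.A) and FAOS is marked on the second-treatment day, so treatment-day values are the natural reading and one sentence settles it. The NRS reference is likewise a missing definition; Figure 2, which was not available in the text reviewed, may supply it.

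A reader might also see a conflict between the one-week pre-study abstention (II.D.1) and the restrictions that begin at enrolment (II.D.5). The two can be read in sequence and are not shown to contradict each other.

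**Conclusion.** The point holds as a measurement mismatch. The first-course baseline for FAOS and the performance tests is taken under a different acetaminophen rule from every follow-up, at a visit also used for selection and up to 21 days before treatment. Without a control group, nothing in the design absorbs the difference.

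Sign and size are unknown. The effect is probably modest for FAOS-Pain because of the one-week recall, and the mismatch is more direct for the performance tests. The coverage figures of 91.5% and 80.5% show what a shift would do if it were 0.1 or 0.2 SD; they do not estimate its size.

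A reader might infer that the trial will overstate benefit, understate it, or miss a real effect on pain. The documents support none of these. The direction is not established, and power for FAOS-Pain remains 98.6% even with an assumed shift of 0.3 SD against benefit. The change is worth making because it is cheap and the second-course schedule already works this way.

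**What to change.** 1. Add the FAOS and both performance tests to Visit 2, before the procedure and before any diagnostic block given that day. The existing hold already covers Visit 2, so no medication rule changes.
2. Define the Visit 2 values as the first-course baseline. Keep the screening FAOS for eligibility, and repeat the primary analysis with the screening baseline as a sensitivity analysis.
3. Record the date of each diagnostic block. Add a sensitivity analysis excluding patients whose block fell within the recall week before Visit 2.
4. As accompanying clarifications, state that treatment-day values taken before the procedure are the second-course baseline. Also state which NRS visit and question form the baseline for the 20% rule, and which question is used at follow-up. The choice of NRS reference is the sponsor's.

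The cost is two schedule marks, one date field, three definitions, two sensitivity analyses and about 13 minutes per patient (8.7 hours for 40), at a visit that already collects NRS. Procedure-day anticipation and possible block influence on recall remain as downsides. Neither baseline removes natural history or expectation effects.

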A FAOS validation study, completed by S.B.Mani et al., confirmed that some FAOS sub-scales (i.e. pain, activities of daily living and quality of life) are valid for independent use. According to the study, the effect size for FAOS pain and quality of life is 1.06, whereas for activities of daily living there is an effect size of 0.65. At an effect size of 0.65 and a single-sized alpha of 0.025, a sample size of 32 would provide a power of 90%. While 80% power is customary, it would be desirable to plan for 90% to reduce the probability of missing an effect if one is present and to provide sufficient power for comparisons at 2-time points. Assuming up to 20% dropout, we plan to recruit 40 participants. This should be more than sufficient, considering that the effect size for the other 2 outcomes has been reported to be 1.06.⁹

D. Subject Criteria (See Vulnerable Populations appendix, if applicable):

Enrollment will be comprised of 40 subjects, age 18 and over with symptomatic ankle OA. There will be no exclusions based on sex or ethnic group. Potential subjects will be identified through hospital records, referrals from physicians in the surrounding community, and mass mailings, or advertisements posted in area clinics and businesses.

1. Inclusion criteria

- Participation in an institutional review board-approved informed consent process, culminating in providing written consent.
- Willingness and ability to comply with the study procedures, visit schedules and ability to follow verbal and written instructions.
- Male or female over 18 years of age.
- Currently Kellgren-Lawrence (KL) Grade 2, 3 or 4 in the ankle based on an X-ray. (weight-bearing mortise views with 20° internal rotation)¹⁰
- Limited by unilateral ankle pain, rated on a Numerical Rating Scale for pain severity as ≥5 on most days over the last month.
- Foot and ankle outcome score (FAOS) of < 75 in at least 1 category.
- Body mass index (BMI) ≤ 50 kg/m²
- Ambulatory.
- Willingness to abstain from the use of protocol-restricted medications during the study and also willing to abstain from using analgesics other than acetaminophen 1 week prior to the beginning of the study.
- Has undergone at least one prior conservative osteoarthritis treatment (e.g. physical therapy, analgesics).

2. Exclusion criteria:

- Baseline knee, hip, spine or other limitations that affect the walking ability to a greater extent than their ankle.

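### For the first treatment, the baseline FAOS and performance tests fall outside the 48-hour acetaminophen hold that covers every follow-up assessment

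*Combined protocol and SAP*

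**What the plan says.** - **Acetaminophen.** Section II.D.4 permits it during the study, described as "Acetaminophen as an occasional rescue medication". Before treatment: "During the screening period (i.e., prior to the procedure visit), subjects may take acetaminophen as needed to a maximum of 3000 mg per day". The hold is then set: "Use of acetaminophen must be discontinued 48 hours prior to the procedure visit and each subsequent scheduled visit". Visit 1 (screening) is not named.
- **Timing, first treatment.** In the section II.E schedule, the FAOS and the physical performance measures are each marked at Visit 1 and at weeks 6, 12 and 24. Their Visit 2 cells are blank. Concomitant medications are marked at Visits 1 and 2 and at weeks 6, 12 and 24.
- **Timing, second treatment.** The second schedule marks the FAOS and the performance measures at the treatment visit itself and again at weeks 6, 12 and 24.
- **Endpoint.** Section II.E makes week-12 FAOS-Pain against baseline the primary endpoint. Section II.C confirms that there is no control group.
- **Other analgesics.** The inclusion criteria (II.D.1) require a participant to be "willing to abstain from using analgesics other than acetaminophen 1 week prior to the beginning of the study". Section II.D.5 lists drugs that "should not be taken or used beginning immediately upon enrollment (after signing informed consent) until the subject reaches the end of the study", but exempts NSAIDs, opioids and centrally acting drugs taken at a stable dose for three months or more. Section II.D.4 also says: "Concomitant treatment for OA will be standardized to oral acetaminophen (e.g. Tylenol) for all subjects during the study".

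**The concern.** In a single-arm study the baseline is half of the effect estimate, and there is no comparator in which a difference in measurement conditions would cancel. If participants may take acetaminophen up to the moment of the baseline assessment but must stop it two days before each follow-up, part of the observed change can reflect analgesic use rather than cryoneurolysis. Aim 1 is to determine how much pain relief follows treatment, so a shift in either direction matters. The second-treatment baseline is taken under the hold, so the two courses also have baselines measured under different rules.

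**Working it through.** **1. Which rule governs each assessment**

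| FAOS and performance tests | Under the 48-hour hold? |
|---|---|
| First-treatment baseline (Visit 1) | No |
| First-treatment weeks 6, 12, 24 | Yes |
| Second-treatment baseline (treatment visit) | Yes |
| Second-treatment weeks 6, 12, 24 | Yes |

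The protocol does not formally define baseline. Visit 1 follows from the schedule, as the only assessment of these measures before the first treatment.

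**2. Does another rule close the gap?** No. The one-week stop in II.D.1 leaves acetaminophen out, and the restricted list in II.D.5 does not include it.

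**3. How much of FAOS-Pain is exposed.** Items P2 to P9 sit under a last-week question; P1 asks about frequency.
- Items: 8 of 9.
- Raw points: 8 × 4 = 32 of 36, and 32/36 = 88.9%.
- Permitted acetaminophen days in the recall week: at most 7 at baseline, and 7 − 2 = 5 at follow-up.
- One response step on one item: 100/36 = 2.78 points.

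These figures describe the exposed part of the score and the ceiling on permitted use. They do not measure bias.

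**4. Performance tests.** The 40 m walk and the balance test are measured at the visit, with no recall period. At follow-up the preceding 48 hours should be free of acetaminophen. At Visit 1 a dose on the same day is permitted.

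**5. Direction.** A higher FAOS-Pain score means less pain. Acetaminophen in the week before Visit 1 would tend to raise the baseline, and the hold would tend to lower the follow-up score. Both reduce the measured improvement.

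**6. Size.** The plan gives no figure on this point: no acetaminophen use and no effect of it on FAOS. The following is therefore an illustration on assumed shifts, not an estimate.
- Reference: the plan's 32 evaluable participants at effect size 0.65 for 90% power. A one-sample t-test gives 90.05% at n = 32 with 0.0125 per tail, and 94.5% with one-sided 0.025. Recruitment: 32/0.8 = 40.
- Let b be the assumed loss of measured improvement, in SDs of change. Power = 1 − F(t critical; 31 df, noncentrality (d − b)√32), where F is the noncentral t distribution function.

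| b | FAOS-Pain, d = 1.06 (0.025 / 0.0125 per tail) | ADL, d = 0.65 (0.025 / 0.0125 per tail) |
|---|---|---|
| 0 | 100% / 100% | 94.5% / 90.0% |
| 0.1 | 100% / 99.8% | 85.4% / 77.1% |
| 0.2 | 99.7% / 99.2% | 69.4% / 58.0% |
| 0.3 | 98.6% / 97.0% | 48.3% / 36.6% |

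At the plan's own effect size, the primary endpoint keeps its power over this range. For FAOS-Pain the issue is the accuracy of the estimated change. The documents do not say which value of b, if any, is realistic.

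**The case against.** The strongest reply is that a difference in permission is not a difference in exposure. Acetaminophen is meant for occasional rescue, the hold removes only two of seven recall days, and a bias against the treatment cannot create a false positive. All of this stands, and it is why the point is modest. It does not remove the mismatch, which the schedule and the hold show directly.

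A second reply is that Visits 1 and 2 may be close together, since the 21-day period in II.B sets no minimum, so a hold before Visit 2 might also cover the days before Visit 1. That would be incidental: the hold is tied to Visit 2, and consent is only given at Visit 1.

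A third reply is that concomitant medications are already recorded at every visit at which the FAOS is taken. This is right and useful. It allows description for participants already treated, but it does not put the baseline under the same rule.

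A reader might also infer that the wording on chronic analgesics inflates the effect: chronic users stop for a week, are measured in worse pain, then resume. The documents do not show this. The inclusion criterion has no stable-dose exemption and II.D.5 has one, so eligibility and drug use of chronic users are unclear. No text sets out a stop before baseline followed by resumption. The criterion also does not define the study's beginning, so it is not clear that the stop covers the Visit 1 recall week.

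**Conclusion.** The concern holds in a limited form. For the first treatment, the baseline FAOS and performance tests are taken without the acetaminophen hold that applies at weeks 6, 12 and 24 and at the second-treatment baseline. Any resulting difference in actual use enters the change from baseline. The effect is probably small, cannot be sized from the documents, and tends to understate improvement.

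This rests on reading Visit 1 as the baseline and on some participants using acetaminophen before it. Comparisons among weeks 6, 12 and 24 are not affected, because those visits share one rule. The documents do not support a claim that the mismatch favours cryoneurolysis, nor one that it threatens power for the primary endpoint. The chronic-analgesic wording is a minor ambiguity about eligibility, with no bias shown. The change is worth making because it is cheap and follows what the protocol already does for the second treatment.

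**What to change.** **Participants not yet treated.** Repeat the FAOS and the performance tests at Visit 2 under the existing hold, and name these as baseline. State that they come before the diagnostic block and the procedure, because the schedule has no row for the block. Keep the Visit 1 FAOS for eligibility only, and do not reapply the criterion "Foot and ankle outcome score (FAOS) of < 75 in at least 1 category" to the Visit 2 score.

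**Participants already treated.** Section II.B mentions remote follow-up in March to May 2020, so there may be some. Keep their Visit 1 baseline, report which baseline each participant has, and describe the concomitant analgesic use already recorded at Visit 1 and week 12.

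**Minor clarification.** Define the study's beginning as used in the inclusion criterion, and state one rule for chronic stable analgesics in II.D.1, II.D.4 and II.D.5.

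**Cost.** Using the protocol's own timings, the three FAOS subscales take 3 + 4 + 2 = 9 minutes and the two performance tests 2 + 2 = 4 minutes, so about 13 minutes per participant, plus protocol wording. The sample size does not change. If some participants are already treated, the analysis will contain two kinds of baseline, which is why they should be identified. No minimum wait between Visits 1 and 2, extra comparison of NRS scores or subgroup description is needed.
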